6.3.2 Serious Adverse Event Reporting (SAE)

6.3.2.1 Internal SAE reporting to IND Office

An adverse event or suspected adverse reaction is considered “serious” if, in the view of either the investigator or the sponsor, it results in any of the following outcomes:

- Death
- A life-threatening adverse drug experience – any adverse experience that places the patient, in the view of the initial reporter, at immediate risk of death from the adverse experience as it occurred. It does not include an adverse experience that, had it occurred in a more severe form, might have caused death.
- Inpatient hospitalization or prolongation of existing hospitalization
- A persistent or significant incapacity or substantial disruption of the ability to conduct normal life functions.
- A congenital anomaly/birth defect.

Important medical events that may not result in death, be life-threatening, or require hospitalization may be considered a serious adverse drug experience when, based upon appropriate medical judgment, they may jeopardize the patient or subject and may require medical or surgical intervention to prevent one of the outcomes listed in this definition. Examples of such medical events include allergic bronchospasm requiring intensive treatment in an emergency room or at home, blood dyscrasias or convulsions that do not result in inpatient hospitalization, or the development of drug dependency or drug abuse (21 CFR 312.32).

- **Important medical events as defined above, may also be considered serious adverse events. Any important medical event can and should be reported as an SAE if deemed appropriate by the Principal Investigator or the IND/IND Sponsor, IND Office.**
- All events occurring during the conduct of a protocol and meeting the definition of a SAE must be reported to the IRB in accordance with the timeframes and procedures outlined in “University of Texas M. D. Anderson Cancer Center Institutional Review Board Policy for Investigators on Reporting Unanticipated Adverse Events for Drugs and Devices”. Unless stated otherwise in the protocol, all SAEs, expected or unexpected, must be reported to the IND Office, regardless of attribution (within 5 working days of knowledge of the event).
- **All life-threatening or fatal events**, that are unexpected, and related to the study drug, must have a written report submitted within **24 hours** (next working day) of knowledge of the event to the Safety Project Manager in the IND Office.
- Unless otherwise noted, the electronic SAE application (eSAE) will be utilized for safety reporting to the IND Office and MDACC IRB.
- **Serious adverse events will be captured from the time of the first protocol-specific intervention, until 30 days after the last dose of drug, unless the participant withdraws consent. Serious adverse events must be followed until clinical recovery is complete and laboratory tests have returned to baseline, progression of the event has stabilized, or there has been acceptable resolution of the event.**
- **Additionally, any serious adverse events that occur after the 30 day time period that are related to the study treatment must be reported to the IND Office. This may include the development of a secondary malignancy.**

6.3.2.2 Reporting to FDA:

- Serious adverse events will be forwarded to FDA by the IND Sponsor (Safety Project Manager IND Office) according to 21 CFR 312.32.

It is the responsibility of the PI and the research team to ensure serious adverse events are reported according to the Code of Federal Regulations, Good Clinical Practices, the protocol guidelines, the sponsor's guidelines, and Institutional Review Board policy.

6.3.2.3 Investigator Communication with Supporting Companies:

The MDACC Internal SAE Report Form will be used for reporting to Merck Global Safety ([contact]), and reporting timeline is as below:

Type of Event	Reporting Time Period: Consent to Randomization/Allocation	Reporting Time Period: Randomization/Allocation through Protocol-specified Follow-up Period	Reporting Time Period: After the Protocol-specified Follow-up Period	Time Frame to Report Event and Follow-up Information to Merck:
Serious Adverse Event (SAE) including Cancer and Overdose	Report if: - due to protocol-specified intervention - causes exclusion - participant is receiving placebo run-in or other run-in treatment	Report all	Report if: - drug/vaccine related. (Follow ongoing to outcome)	Within 2 business days but no longer than 3 calendar days of receipt of information
Pregnancy/Lactation Exposure	Report if: - participant has been exposed to any protocol-specified intervention (eg, procedure, washout or run-in treatment including placebo run-in) Exception: A positive pregnancy test at the time of initial screening is not a reportable event.	Report all	Previously reported – Follow to completion/termination; report outcome	Within 2 business days but no longer than 3 calendar days of receipt of information
Event of Clinical Interest (require regulatory reporting)	Report if: - due to intervention - causes exclusion	Report - potential drug-induced liver injury (DILI) - require regulatory reporting	Not required	Within 2 business days but no longer than 3 calendar days of receipt of information

Events of clinical interest (ECI) for this trial include:

1. An overdose of MK-3475 that is not associated with clinical symptoms or abnormal laboratory results. For purposes of this study, an overdose of MK-3475 will be defined as any dose of 1,000 mg or greater. No specific information is available on the treatment of overdose of pembrolizumab. In the event of overdose, the participant should be observed closely for signs of toxicity. Appropriate supportive treatment should be provided if clinically indicated.
2. An elevated AST or ALT lab value that is greater than or equal to 3X the upper limit of normal and an elevated total bilirubin lab value that is greater than or equal to 2X the upper limit of normal and, at the same time, an alkaline phosphatase lab value that is less than 2X the upper

limit of normal, as determined by way of protocol-specified laboratory testing or unscheduled laboratory testing.*

*Note: These criteria are based upon available regulatory guidance documents. The purpose of the criteria is to specify a threshold of abnormal hepatic tests that may require an additional evaluation for an underlying etiology.

6.3.4 Evaluating Adverse Events

An investigator or a designee will evaluate and record adverse events according to the NCI Common Terminology for Adverse Events (CTCAE), version 4.0 as standard practice per institution guidelines.

7.0 STATISTICAL ANALYSIS PLAN

The primary objective of this phase II trial is to assess the efficacy of MK-3475 as a single agent in metastatic IBC and non-IBC TNBC patients. The primary endpoint is the rate of disease control measured at the end of 4 months from the start of therapy.

The disease control rate is defined as the percentage of patients either 1) with measurable disease that achieve iCR, iPR, iSD, or 2) with non-measurable disease that achieve iCR or iSD, , by 4 months or more in all evaluable patients. We will also perform secondary analysis on intent-to-treat patient population where those patients who drop out early will be considered as progression.

The trial will be conducted using Simon's optimal two-stage design and the rate of disease control will be estimated accordingly. It is assumed that the MK-3475 single agent will have a disease control rate of 30%. A disease control rate of 10% or lower will be considered treatment failure and the regimen will be rejected under this circumstance. When the probability of accepting a "bad" regimen (i.e. disease control rate 10% or lower) is 0.10 and the probability of rejecting a "good" regimen (i.e. disease control rate 30% or higher) is also 0.10, Simon's optimal 2-stage design requires 12 patients enter in the first stage. The study accrual will be delayed until all 12 patients are evaluable for disease control status. If 1 or no patients maintain disease control on treatment, the trial will be stopped and the regimen will be declared as ineffective. If 2 or more patients maintain disease control, 23 more patients will be enrolled to the study to reach a total of 35 treated patients. By the end of the study, the new regimen will be rejected if rate of disease control is less than or equal to 5/35 and will be considered worthy of further investigation otherwise.

However, with a larger sample size, we will be able to detect a smaller target disease control rate of 0.25. It is assumed that the MK-3475 single agent will have a disease control rate of 25%. A disease control rate of 10% or lower will be considered treatment failure and the regimen will be rejected under this circumstance. When the probability of accepting a "bad" regimen (i.e. disease control rate 10% or lower) is 0.10 and the probability of rejecting a "good" regimen (i.e. disease control rate 25% or higher) is also 0.10, Simon's optimal 2-stage design requires 21 patients enter in the first stage. The study accrual will be delayed until all 21 patients are evaluable for disease control status. If 2 or less patients maintain disease control on treatment, the trial will be stopped

and the regimen will be declared as ineffective. If 3 or more patients maintain disease control, 29 more patients will be enrolled to the study to reach a total of 50 treated patients. By the end of the study, the new regimen will be rejected if rate of disease control is less than or equal to 7/50 and will be considered worthy of further investigation otherwise. But, that will not happen based on the current disease control rate.

At any time after first 5 patients are treated, if $\geq 30\%$ patients experience serious adverse events (SAE) within 2 cycles of treatment, we will stop the trial and claim that the regimen is too toxic. SAE is defined as an adverse event is serious, unexpected, and related to the study drug.

Patients' characteristics will be summarized at the end of the study. For discrete or categorical data, descriptive statistics will be generated including tabulations of frequencies. For continuous data, summary statistics including sample size, mean, standard deviation, median, minimum and maximum will be computed. A 95% exact binomial confidence interval on disease control rate will be computed.

Various biomarker endpoints will be measured in various specimens. Correlation among biomarkers at baseline in each specimen and between different specimens will be assessed. The association among various continuous and discrete biomarkers or disease status groups will be assessed by the exploratory data analysis using scatter plot matrix, box plots, BLIP plot³⁷ and trellis plot, etc, and may be tested by t-test/ANOVA/Wilcoxon rank sum test/Kruskal-Wallis test, whichever is appropriate. Correlation between continuous biomarkers will be examined by Pearson or Spearman rank correlation coefficients. The association between discrete biomarkers will be tested by chi-square or Fisher's exact test. Paired t-test/Wilcoxon rank sum test and McNemar's test may be used to test the change of a single continuous biomarker and discrete biomarker, respectively, over time within each treatment group. Repeated measures analysis including mixed effects model will be performed to analyze the correlation between disease control and biomarkers change over time.³⁸ Disease control survival and overall survival time from the registration date will be estimated using Kaplan-Meier method.

All statistical tests will be performed at a two-sided significance level of 5% using SAS or S-Plus, as appropriate.

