3.1.7 Study Endpoint

Most patients with metastatic IBC who achieved a maximum tumor response by standard chemotherapies will eventually have disease progression within 4 months. The goal of this clinical trial is to observe clinical activity signals of MK-3475 for disease stabilization or control as a maintenance therapy after achieving a maximum tumor response by standard chemotherapy. The efficacy endpoint is to evaluate the rate of patients who remain progression free at the end of 4 months from the maximum tumor response after receiving MK-3475³⁶.

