4.1.1 Inclusion Criteria

1. Is willing and able to provide written informed consent for the trial.
2. Is a female or male and ≥ 18 years of age
3. Has histological confirmation of HER2 normal breast carcinoma with a clinical diagnosis of IBC based on presence of inflammatory changes in the involved breast, including diffuse erythema and edema (peau d'orange), with or without an underlying palpable mass involving the majority of the skin of the breast. Pathological evidence of dermal lymphatic invasion should be noted but is not required for diagnosis of inflammatory breast cancer regardless of ER/PR status

OR

Has histological confirmation of triple negative breast carcinoma (HER2 normal, ER/PR $< 10\%$) without clinical diagnosis of IBC

4. Has stage IV or recurrent disease that has been treated.
5. Has clinical response or stable disease for minimum of two months (three cycle of every three week chemo or 8 weeks of weekly regimen, etc.) after receiving any prior chemotherapy for metastatic/recurrent disease. A minimum of two cycles (6-8 weeks) of chemotherapy is required to determine clinical response.

Per RECIST criteria 1.1, Clinical response for *measurable disease* is defined as complete response (CR) or partial response (PR); for *non-measurable disease only* (i.e. bone metastasis, ascites, pleural effusion, and pathological lymph nodes ≥ 10 to <15 mm short axis) is defined as persistence of one or more non-target lesion(s) and no increase in overall tumor burden.

6. Is HER2 normal, defined as HER2 0 or 1+ by IHC and negative by FISH if performed; or HER2 is 2+ by IHC and negative by FISH; or HER2 negative by FISH if IHC is not performed.
7. Has a performance status of 0-1 on the ECOG Performance Scale.
8. Has adequate organ function as determined by the following laboratory values:

ANC \geq 1000 /mcL, Platelets \geq 100,000 /mcL, Hgb \geq 9 g/dL, creatinine levels $<$ 1.5 x ULN, Total bilirubin \leq 1.5 x ULN, ALT and AST \leq 2.5 x ULN or \leq 5 x ULN for subjects with liver metastases.

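### The formal definition of the primary disease control rate is garbled and conflicts with the endpoint sentence, the stage rules and Section 3.1.7; one available reading would count early stable disease followed by progression as success.

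*Combined protocol and SAP*

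**What the plan says.** Section 7.0 first gives the endpoint as the "rate of disease control measured at the end of 4 months from the start of therapy". The definition that follows counts patients "with measurable disease that achieve iCR, iPR, iSD", or, for non-measurable disease, iCR or iSD, and closes with "by 4 months or more in all evaluable patients". It gives no minimum duration for iSD and no assessment date or window.

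The stopping rule for the first stage uses a different verb: "If 1 or no patients maintain disease control on treatment". The 50-patient version uses the same verb. Neither rule names a month.

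Section 3.1.7 describes the efficacy endpoint as "the rate of patients who remain progression free at the end of 4 months from the maximum tumor response". That is a maintained-control endpoint, but with a different starting point from Section 7.0. The hypothesis in Section 2.1 is also about maintaining control.

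Inclusion criterion 5 in Section 4.1.1 sets the entry state: "Has clinical response or stable disease for minimum of two months". In Section 4.6.1, Table 4 requires no confirmation of stable disease, and Table 5 assigns iSD as a response at a single timepoint.

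**The concern.** The sentence that decides who is a success is the only one built on *achieve* and *by*; the related passages speak of status at month 4, of maintaining control, or of remaining free of progression. If *by* is taken as a deadline, one iSD at any scan up to month 4 is enough, and later progression before month 4 does not undo it.

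In a trial of patients with growing disease, that would be an ordinary best-response endpoint. Here patients enter already controlled, so iSD at an early scan largely repeats the entry criterion. The 10% failure rate and the 25% and 30% targets fit only control that lasts to month 4; Section 3.1.7 explains a low reference rate by saying that most metastatic IBC patients progress within that time. Two analysts following the text could count different patients, and the decision at stage 1 or at the end could differ.

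**Working it through.** **1. The plan's own designs.** Inputs from Section 7.0: p0 = 0.10; p1 = 0.30 with r1/n1 = 1/12 and r/n = 5/35; p1 = 0.25 with r1/n1 = 2/21 and r/n = 7/50; both error limits 0.10.

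The probability of declaring the regimen worthy at true rate p is

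P(p) = Σ over x from r1+1 to n1 of Bin(x; n1, p) × Pr[Bin(n − n1, p) > r − x].

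- 35-patient rule: P(0.10) = 0.0977, P(0.30) = 0.9014.
- 50-patient rule: P(0.10) = 0.0979, P(0.25) = 0.9008.

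An exhaustive search for the design with the smallest expected size under p0 returns exactly these two designs. The Simon figures are right if a success is control maintained to month 4.

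**2. What if one earlier iSD is enough?** The share without progression cannot rise with time. If 10% are controlled at month 4, at least 10% are controlled at any earlier scan, so under this reading the error cannot fall below the 0.098 of step 1. Its size depends on the share s with iSD at the qualifying scan. With no assumption about timing:

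| s | 35-patient rule | 50-patient rule |
|---|---|---|
| 0.15 | 0.337 | 0.407 |
| 0.20 | 0.604 | 0.725 |
| 0.30 | 0.901 | 0.969 |
| 0.50 | 0.997 | 0.9999 |

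**3. Linking s to a scan week.** These are assumptions, not statements in the documents: a constant progression hazard and one qualifying scan at week t. Four months is 4 × 30.4375 / 7 = 17.39 weeks, so s(t) = S4^(t/17.39), where S4 is the true 4-month control rate.

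| Scan week | s, S4 = 10% | P, 35 / 50 patients | s, S4 = 5% | P, 35 / 50 patients |
|---|---|---|---|---|
| 3 | 0.672 | >0.999 / >0.999 | 0.596 | 0.9997 / >0.999 |
| 6 | 0.452 | 0.992 / 0.9995 | 0.356 | 0.959 / 0.992 |
| 9 | 0.304 | 0.907 / 0.971 | 0.212 | 0.659 / 0.782 |
| 12 | 0.204 | 0.624 / 0.746 | 0.127 | 0.212 / 0.243 |

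The comparison value is 0.098 at a true rate of 10%.

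**4. Scan timing.** The flow chart in Section 5.0 marks imaging at alternate three-week cycles. Cycle c starts at week 3(c − 1). Even cycles would give weeks 3, 9, 15 and 21; odd cycles from cycle 3 would give weeks 6, 12 and 18. The column positions are uncertain in the extracted text: the correlative-blood row shows the same alternating pattern over cycles 1 to 8, yet its footnote names cycles 3, 6 and 9. The table in step 3 therefore covers a range of weeks.

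**The case against.** The strongest reply is that the intended meaning is clear enough. The words *or more* have no function if the phrase is a deadline, but make sense if it is a duration. The preceding sentence fixes the time point, the stage rules speak of maintaining control, and Sections 2.1, 3.1.7 and 4.6 describe maintenance. The secondary intent-to-treat analysis in Section 7.0 counts early drop-outs as progressors, which fits status through month 4 better than best response. The 10% reference rate itself makes sense only for maintained control.

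Most of this stands, and it makes maintained control the likelier intention. It does not settle the count. The definition is the formal statement of the numerator, no sentence says which passage takes precedence, and no iSD duration is given anywhere.

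A reader might go further and infer that the plan has adopted a best-response rule, that an ineffective drug would pass almost automatically, or that every patient qualifies at the first scan. The documents do not support these readings. Best response is one reading of a garbled phrase. The inflation figures depend on that reading, on the hazard assumption and on the scan week. Patients who have progressed by the qualifying scan would not count: on the stated assumptions with S4 = 10%, that is about 33% at week 3 (1 − 0.672) and 70% at week 9 (1 − 0.304). Section 7.0 also mentions a current disease control rate, but does not say how it was counted, so it is not evidence that the looser rule was used.

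**Conclusion.** The concern holds as a conflict in the definition of the primary numerator, and it should be resolved because the definition drives both the stage-1 stop and the final decision. There is no error in the Simon designs: under maintained control both keep type I error at 0.098 and power at 0.90.

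If one early iSD were accepted instead, a regimen with a true 4-month rate of 10% would be declared worthy with probability above 0.999 at week 3, at least 0.99 at week 6, 0.91 to 0.97 at week 9 and 0.62 to 0.75 at week 12. These figures show the size of the exposure under a constant hazard and one qualifying scan. They are not the plan's operating characteristics. At a true rate of 5% with a week-12 scan, the probability is 0.21 to 0.24. That the looser reading cannot lower the error follows without the hazard assumption.

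**What to change.** Replace the numerator in Section 7.0 with: patients alive with iCR, iPR or iSD (or the non-measurable equivalent) at the assessment nearest 4 months from the start of therapy, within a stated window, with no progression from first dose through that assessment. Then:

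- State that iSD at an earlier scan followed by progression before month 4 is a failure.
- State how iUPD still unconfirmed at month 4 is counted.
- Choose the window to fit the existing scan schedule. Month 4 is about week 17.4, and the flow chart may place no scan at that week.
- Use the same rule for the interim and final counts.
- Reconcile the time origin: Section 3.1.7 counts from maximum response, Section 7.0 from the start of therapy.

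The cost is a short rewrite of one definition and alignment of Section 3.1.7. The cut-offs and sample sizes stay as they are. The reported rate may be lower than under the any-scan reading. Imaging is done as clinically indicated and per standard of care, so the sponsor should check that enough patients have a scan inside the chosen window.

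### The final cut-offs 5/35 and 7/50 are set on treated patients but the primary rate is taken in evaluable patients; applied as a rate, as worded, the rule does not hold its 0.10 type I error

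*Combined protocol and SAP*

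**What the plan says.** Section 7.0 measures the primary disease control rate "by 4 months or more in all evaluable patients". It then adds: "We will also perform secondary analysis on intent-to-treat patient population where those patients who drop out early will be considered as progression".

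Section 4.6.2 lists who is not evaluable: deaths in the first two weeks from concurrent disease, patients lost to follow-up, and major protocol violators (including ineligible patients). The first two groups are counted as failures in the intent-to-treat analysis. Nothing equivalent is said for violators.

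Section 7.0 uses Simon's "optimal two-stage design and the rate of disease control will be estimated accordingly". Two designs follow, each with a 10% null and both error rates at 0.10:

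- **Target 30%.** Stage 1 has 12 patients and stops at 1 or fewer controlled: "The study accrual will be delayed until all 12 patients are evaluable for disease control status". Then "23 more patients will be enrolled to the study to reach a total of 35 treated patients". At the end the regimen is "rejected if rate of disease control is less than or equal to 5/35".
- **Target 25%.** Stage 1 has 21 patients and stops at 2 or fewer controlled: "The study accrual will be delayed until all 21 patients are evaluable for disease control status". Then "29 more patients will be enrolled to the study to reach a total of 50 treated patients", with a final cut-off of 7/50. Section 1.0 gives 50 as the number of subjects.

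The documents do not say whether non-evaluable patients are replaced, whether the cut-off moves when the evaluable number falls short, or whether 5/35 and 7/50 are counts or proportions.

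**The concern.** The numerator and denominator of the primary rate come from one set of patients, while the cut-off's denominator is the size of another. Once a treated patient is not evaluable, the rule has two readings:

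- **Rate:** divide controlled by evaluable patients and compare the proportion with 5/35 or 7/50. Then 7/49 or 5/34 passes.
- **Count:** 5 or 7 controlled patients is a rejection whatever the denominator.

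The go/no-go decision can therefore turn on a choice that the plan does not make. With 7 controlled of 49 evaluable, the regimen passes as a rate and fails as a count. It also fails in the planned intent-to-treat analysis if the fiftieth patient is counted there as a failure. The reported rate and its exact 95% interval depend on the same unsettled denominator.

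**Working it through.** **Inputs (Section 7.0).** Null p0 = 0.10. For the 50-patient design, n1 = 21, r1 = 2, N = 50, r = 7, p1 = 0.25. For the 35-patient design, n1 = 12, r1 = 1, N = 35, r = 5, p1 = 0.30. The documents give no expected non-evaluable number or share, so those are assumed and shown as a range.

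**Formula.** With n2 = N − n1,

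P(pass) = Σ over x from r1+1 to n1 of P(Bin(n1, p) = x) × P(Bin(n2, p) ≥ r + 1 − x).

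**Step 1: the plan's own figures.** At p = 0.10 this gives alpha 0.0979 (50) and 0.0977 (35). At the target it gives power 0.9008 and 0.9014. A search over all two-stage designs for the smallest expected size under the null returns the same two designs. The plan's figures are correct when every patient is evaluable.

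**Step 2: a fixed number k of stage-2 exclusions, unrelated to outcome.** Stage 1 is complete and n2 becomes n2 − k. On the rate reading, the smallest passing X satisfies X/(N − k) > r/N. For k = 1, 7/49 = 0.143 > 0.140 and 5/34 = 0.147 > 0.143, so the required number falls from 8 to 7 and from 6 to 5. For k = 8 it falls again, since 6/42 = 0.143 and 4/27 = 0.148. On the count reading the requirement stays at 8 or 6.

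| k | Alpha, rate (50 / 35) | Alpha, count (50 / 35) |
|---|---|---|
| 0 | 0.098 / 0.098 | 0.098 / 0.098 |
| 1 | 0.158 / 0.167 | 0.091 / 0.090 |
| 2 | 0.151 / 0.158 | 0.085 / 0.082 |
| 4 | 0.135 / 0.140 | 0.072 / 0.068 |
| 7 | 0.111 / 0.112 | 0.054 / 0.048 |
| 8 | 0.182 / 0.197 | 0.049 / 0.042 |

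The rate reading stays above 0.10 throughout. Power on the count reading with one exclusion is 0.896 / 0.898.

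**Step 3: a random share e of non-evaluable patients in both stages, none replaced, unrelated to outcome.** Each treated patient is controlled with probability 0.10(1 − e), non-evaluable with probability e, and otherwise not controlled. Stage 1 uses its counts. With M non-evaluable in total, the final pass is X/(N − M) > r/N (rate) or X > r (count).

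| e | Alpha, rate (50 / 35) | Alpha, count (50 / 35) |
|---|---|---|
| 1% | 0.119 / 0.116 | 0.094 / 0.094 |
| 2% | 0.130 / 0.128 | 0.090 / 0.091 |
| 5% | 0.134 / 0.140 | 0.078 / 0.081 |
| 10% | 0.120 / 0.130 | 0.061 / 0.066 |
| 20% | 0.115 / 0.116 | 0.035 / 0.042 |

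**Step 4: if every excluded patient is a failure.** With 10% of treated patients controlled, one stage-2 exclusion on the rate reading gives a pass probability of 0.166 / 0.176. Shares of 1%, 5% and 10% give 0.124, 0.161, 0.174 (50) and 0.120, 0.162, 0.175 (35). These are type I errors only if the 10% null refers to treated patients.

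**The case against.** The strongest reply is that nobody using Simon's design would read 5/35 as a proportion. The section invokes that design, both stage-1 rules are counts, and 5/35 and 7/50 are the usual way of writing its final boundaries. On that reading alpha is at most 0.098. This has force and limits the claim: the inflation belongs to one reading. It does not remove the gap, because the sentence names a rate and the section defines that rate in evaluable patients.

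Other points in the plan's favour:

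- The stage-1 pause may mean that 12 or 21 evaluable patients are assembled before the interim decision. The sentence does not state replacement, and it does not reach stage 2. If it is read that way, Step 2 applies rather than Step 3.
- The early-death category is narrow, and the documents do not support any particular share; 10% and 20% are only the upper part of a range.
- Section 7.0 remarks after the 50-patient rule that the outcome it describes will not arise at the current disease control rate. This may mean that the boundary is not close. It does not define the denominator.
- The failure-imputed analysis is already planned, so disagreement between the two analyses would be visible. The plan does not say which would then decide.

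Two stronger inferences are not supported. A reader might take 0.158 / 0.167 as the trial's type I error; it is the highest value for 1 to 7 stage-2 exclusions and holds only on the rate reading. A reader might also conclude that the evaluable analysis is biased upward. Leaving out early deaths and losses does raise the rate relative to all treated patients. It is bias only if the 10% null refers to treated patients, and the plan defines the rate in evaluable ones. For violators, whose outcomes may be observed, the direction is unknown.

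**Conclusion.** The point holds as an unresolved decision rule and should be fixed before the final analysis. Applied as worded, a rate among evaluable patients against 5/35 or 7/50, the rule does not hold 0.10. Alpha is about 0.115 to 0.140 over assumed shares of 1% to 20%. By number of stage-2 exclusions, it runs from 0.158 down to 0.111 (50) or 0.167 down to 0.112 (35) for 1 to 7, and rises to 0.182 / 0.197 at 8. Applied as counts, the rule is slightly conservative.

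These figures assume exclusion unrelated to outcome and a true rate of 10% among evaluable patients. Confidence is high that the text is silent and that the arithmetic is right. Which reading the trial team would use cannot be told from the documents.

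**What to change.** State the boundaries as counts on all patients who received MK-3475: continue with at least 3 of 21 and call the result positive with at least 8 of 50; or at least 2 of 12 and 6 of 35. In that analysis:

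- Count early death, loss to follow-up and no 4-month assessment as not controlled.
- Say how major violators count. A workable rule is that those who added another anti-cancer treatment before the 4-month assessment are not controlled, and other violators count by their observed outcome.
- Keep the evaluable analysis as a sensitivity analysis.
- State whether the 10% null and the target rate refer to treated or evaluable patients.

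A replacement rule alone would restore 0.10 only for exclusions unrelated to outcome.

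Section 4.6.2.3 makes a delay of 7 days or more without administrative reason a violation, while Sections 4.2.1 and 4.2.2 permit longer intervals for toxicity. These passages must be reconciled so that the evaluable set is clear.

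The cost is wording; the failure-imputed analysis is largely planned already. The reported rate will be slightly lower. If null and target refer to treated patients, alpha stays at 0.098 and power at 0.90. If they refer to evaluable patients, the rule is conservative: at 5% non-evaluable, alpha is 0.078 / 0.081 and power about 0.87 / 0.88 (50 / 35); at 10%, power is about 0.83 / 0.85. The SAP should state this.

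### Section 7.0 gives two full Simon rules for one primary endpoint, withdraws neither, and does not say whether the stop at 12 patients still applies if the trial runs to 50

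*Combined protocol and SAP*

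**What the plan says.** Section 7.0 defines one primary endpoint, the disease control rate at 4 months, and names Simon's optimal two-stage design. It then gives two rules. Both use an unacceptable rate of 10% and error probabilities of 0.10 and 0.10.

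- **First rule, target 30%.** "The study accrual will be delayed until all 12 patients are evaluable for disease control status". The trial stops if 1 or none of the 12 has disease control. Otherwise "23 more patients will be enrolled to the study to reach a total of 35 treated patients", and at the end "the new regimen will be rejected if rate of disease control is less than or equal to 5/35".
- **Second rule, target 25%.** It is introduced by "However, with a larger sample size, we will be able to detect a smaller target disease control rate of 0.25". Then "The study accrual will be delayed until all 21 patients are evaluable for disease control status". The trial stops if 2 or fewer of the 21 have disease control. Otherwise "29 more patients will be enrolled to the study to reach a total of 50 treated patients", and at the end "the new regimen will be rejected if rate of disease control is less than or equal to 7/50".

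Directly after the second rule comes the remark "But, that will not happen based on the current disease control rate". Section 1.0 (Trial Summary) gives the number of subjects as 50. Section 7.0 also plans an exact 95% binomial confidence interval for the disease control rate.

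**The concern.** Both rules are written as instructions, and each has its own accrual hold, futility stop, total and final cut-off. Nothing says that the second replaces the first. A total of 50 suggests the second final cut-off but does not show whether the look was at 12, at 21 or at both.

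The two looks can give opposite instructions. With 2 successes in the first 12 and still 2 at 21, the first rule continues and the second stops. With 1 in the first 12 and 3 at 21, the first rule stops and the second continues.

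At stake is the go/no-go decision on the primary endpoint. A reader cannot tell which interim stop was binding, or whether the 0.90 power quoted for a 25% rate describes the trial that was run.

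**Working it through.** **Inputs, all from Section 7.0.** Null rate 0.10; targets 0.30 and 0.25; stop at 1 or fewer of 12, reject at 5 or fewer of 35; stop at 2 or fewer of 21, reject at 7 or fewer of 50. Write X_n for the number with disease control among the first n patients. Patients are taken as independent with a common rate p.

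**Formula.** For a first stage n1 with bound r1 and a total n with bound r:

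P(accept) = sum over x from r1+1 to n1 of P(X_n1 = x) × P(Bin(n − n1, p) ≥ r + 1 − x).

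With two looks, the same sum runs over patients 1–12, 13–21 and 22–50, keeping only paths that pass each look.

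**Step 1: reproduce the plan.** A search for the smallest expected sample size at p = 0.10, with both errors at most 0.10, returns exactly the two designs in Section 7.0.

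| Design alone | Alpha (p = 0.10) | Power at 25% | Power at 30% |
|---|---|---|---|
| 12, then at least 6/35 | 0.098 | 0.795 | 0.901 |
| 21, then at least 8/50 | 0.098 | 0.901 | 0.969 |

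Each meets its own claim, so there is no arithmetic error in either.

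**Step 2: end at 50 and vary the looks.** The plan writes out neither of these combinations. They are what results if the stop at 12 is kept.

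| Path | Alpha | Power at 25% | Power at 30% |
|---|---|---|---|
| Look at 12 only, then at least 8/50 | 0.083 | 0.820 | 0.911 |
| Looks at 12 and 21, then at least 8/50 | 0.077 | 0.807 | 0.905 |

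**Step 3: why power at 25% falls.** At p = 0.25 the stop at 12 is triggered with probability

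0.75^12 + 12 × 0.25 × 0.75^11 = 0.0317 + 0.1267 = 0.158.

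Any path that includes this look therefore has power of at most 1 − 0.158 = 0.842, whatever follows. The look at 21 stops with probability 0.0745, so it is passed with probability 0.9255; both looks are passed with probability 0.8242. The difference, 0.9255 − 0.8242 = 0.101, is the chance at a true 25% that the second rule would continue a trial which the first rule had stopped.

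The loss against the stated design is 0.901 − 0.820 = 0.081 with the look at 12 alone, and 0.901 − 0.807 = 0.094 with both.

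**Step 4: what does not change.** An added futility stop can only lower the chance of acceptance, so adding the look at 12 to the 21/50 design cannot raise alpha. Computed alpha is below 0.10 on both paths in Step 2, and power at 30% is above 0.90 on both.

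**The case against.** The strongest reply is that the documents largely answer the question. Only the second design reaches the 50 subjects in Section 1.0, and its opening sentence moves from a smaller design to a larger one. That stands: the natural reading is that 7/50 is the final cut-off. It does not settle the interim looks, because the stop at 12 is never withdrawn.

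Three stronger readings are tempting, and the documents do not support them.

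- **That the two final cut-offs are equally live, so that 6/35 is a success and 7/50 a failure.** A trial that ends at 35 has no further 15 patients, and one that ends at 50 does not decide at 35. Applied to the same patients, the full rules differ with probability 0.135 at a true 25%. Of that, 0.9154 − 0.7947 = 0.121 is acceptance by 21/50 alone, which mostly reflects the larger design's greater power.
- **That the type I error exceeds 0.10.** Counting success under either full rule would give 0.135, and accepting at 35 after a look at 21 would give 0.117. The plan allows neither.
- **That the second design was chosen because of results.** The remark on the current disease control rate suggests that some outcome data were in hand when it was written. The rate is not defined, it is unclear what the sentence says will not happen, and nothing ties the choice of design to it.

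**Conclusion.** Wrong as written, and it should be fixed. Section 7.0 contains two unreconciled decision rules for the primary endpoint. On the natural reading the trial ends at 50 with rejection at 7 or fewer, and the open question is whether the look at 12 applied. If it did, power at 25% is 0.820 (in place of the look at 21) or 0.807 (with both looks), against the stated 0.90. Alpha and power at 30% remain within the stated limits on either path.

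These figures rest on independent patients, a common rate, complete 4-month assessment and a path fixed without regard to outcomes. If the path was chosen after results were seen, none of them applies as it stands.

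The exact 95% interval is still planned, so the problem is confined to the decision rule and its error rates.

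**What to change.** Changes to Section 7.0, wording only:

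1. Record the rule actually in force, which on the natural reading is 21/50 with rejection at 7 or fewer. Mark the 12/35 rule as superseded. Give the date of that change, and how many patients were evaluable and how many had disease control at that time. This should be a record of what was in force and not a fresh choice between the two, since outcomes may already be known.
2. State which interim looks apply or were applied (12, 21 or both), and restate exact alpha and power at 25% and at 30% for that path.
3. Clarify and date the remark that follows the second rule: what it refers to, and what data had been seen. Then take it out of the decision rule. Deleting it without explanation would remove the only hint that data had been seen.

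**Cost.** No extra patients and no new analysis. The stated power at 25% may have to come down from 0.90 to 0.82 or 0.81. If 21 was the sole look and the path was fixed without regard to outcomes, no figure changes.
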